6.3 Adverse Events Definition and Reporting

Study investigators will be able to remove patients from the trial based on their clinical discretion and specific patient outcomes. Any adverse events, including grading of severity and attribution to research will be reported.

In this study, AEs will be defined as any event associated with virtual presentation and follow-up sessions whether or not considered intervention related. This includes any physical, psychological or emotional harm, or any other unintended effects experienced by the participant. Adverse events will be considered from the time of consent and will be monitored and recorded throughout the study. AEs evaluation will be done 24 hours after the first treatment and within 72 hours after 8th treatment. Participants will be asked to report any AEs they experience, either spontaneously or during the study visits. AEs will be recorded on the appropriate CRF. Patients will be closely monitored for adverse events.

The following adverse events will be collected from the time of randomization for the study:

- Adverse events that are not listed in the current labeling for esketamine. This includes events that are similar to those on the labeling but differ from the event because of greater severity or specificity.
- Study Treatment Discontinuation Adverse Events
- Events that lead to the discontinuation of esketamine will be collected for the study. These events will be recorded on either an AE or an SAE form.

The study team will document the AEs, its severity, relationship to the intervention, and the actions taken to address it.

An adverse event (AE) or suspected adverse reaction is considered "serious" if, in the view of either the investigator or sponsor, it results in any of the following outcomes: death, a life-threatening adverse event, inpatient hospitalization or prolongation of existing hospitalization, a persistent or significant incapacity or substantial disruption of the ability to conduct normal life functions, or a congenital anomaly/birth defect.

Note: In addition to AEs as described above, a separate side effect form will be collected during the trial which will solely focus on known side effects of esketamine as per the current labeling (See appendix 2).

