6.4 Reaction Management

Reaction management refers to the actions taken to manage any adverse events (AEs) that occur during the study. In the event that a participant experiences an AE, the study team will take appropriate measures to manage the reaction, minimize harm, and ensure the safety and well-being of the participant.

The first step in reaction management is to identify and document the AE. Participants will be asked to report any AEs they experience, either spontaneously or during the study visits.

The study team will document the AE, its severity, relationship to the intervention, and the actions taken to address it.

Based on the severity of the AE, the study team may take various actions to manage the reaction. For minor AEs, such as mild nausea or headache, the study team may provide advice or over-the-counter medications to alleviate the symptoms. For more serious AEs, such as hospitalization, the study team will take immediate action to ensure the safety and well-being of the participant.

If necessary, the study team may discontinue the intervention for a participant experiencing a serious adverse event. Participants who experience a serious adverse event will be referred to their treating physician or a specialist for further evaluation and management.

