8.7 Data and Safety Monitoring Plan

We do not anticipate any adverse events. The principal investigator (PI) will monitor the data, assure protocol compliance, and conduct the safety reviews at least annually. The PI evaluates whether the study should continue unchanged, require modifications, or close to enrollment. Any Reportable Events (which are events that are serious or life-threatening and unanticipated (or anticipated but occurring with a greater frequency than expected) and possibly, probably, or definitely related) Unanticipated Problems Involving Risks to Subjects or Others (UPIRSO) will be reported to the IRB and any appropriate funding and regulatory agencies. Unanticipated Problems Involving Risks to Subjects or Others that may require a temporary or permanent interruption of study activities (if possible) will be reported, followed by a written report within 5 calendar days of my becoming aware of the event to the IRB and any appropriate funding and regulatory agencies. The PI will apprise fellow investigators and study personnel of all UPIRSOs and adverse events that occur during the conduct of this research project. The PI will report all UPIRSOs and adverse events that occur during the conduct of this research project to other applicable oversight bodies as required within applicable reporting timeframes.

9 Study Considerations

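### The list in section 6.3 of adverse events to be collected conflicts with the plan's other safety text and does not expressly require that all serious events be collected

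*Combined protocol and SAP*

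**What the plan says.** Section 6.3 introduces a list with "The following adverse events will be collected from the time of randomization for the study". Its first item is "Adverse events that are not listed in the current labeling for esketamine", extended by "This includes events that are similar to those on the labeling but differ from the event because of greater severity or specificity". The other items concern stopping treatment: "Events that lead to the discontinuation of esketamine will be collected for the study". An SAE form is mentioned in 6.3 only for these discontinuation events. The section goes on to define what makes an event serious, but no item on the list uses that definition.

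The same section also contains general sentences: "Any adverse events, including grading of severity and attribution to research will be reported", and "Adverse events will be considered from the time of consent and will be monitored and recorded throughout the study". Its AE definition refers to events associated with the virtual presentation and the follow-up sessions. The Glossary definition adds events associated with esketamine treatment. A closing note in 6.3 says that known labelled effects go on a separate form (Appendix 2), in addition to the AEs.

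Section 6.4 gives examples of AEs and their handling, beginning "For minor AEs, such as mild nausea or headache", and names hospitalization as a more serious one. Section 8.7 says that the PI reports all adverse events. It also makes serious, at least possibly related events reportable if they are unanticipated, or "anticipated but occurring with a greater frequency than expected".

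**The concern.** Section 2.2 names a change in effectiveness and in side effects as the main risk of the study intervention. Events of labelled types are therefore where harm would be expected to show. If staff work from the 6.3 list, a labelled-type event that meets a seriousness criterion has no item requiring it to be collected, provided that the patient stays on esketamine and the event is no more severe or specific than the label. If staff work from the general sentences, it is collected. The two instructions can give different safety data from the same patients, and the definition that would settle the matter is worded around sessions that only one arm attends.

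Section 7.6 provides for no external monitoring, and 8.7 has the PI review safety at least annually. The trial's own records are therefore the main basis for noticing a problem, and for applying the frequency rule in 8.7.

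**Working it through.** No figure in the plan bears on this point, so the check is a comparison of the texts.

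**Scope, start point and definition side by side**

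| Place | What is covered | From when |
|---|---|---|
| 6.3, list | Unlabelled events; labelled types of greater severity or specificity; events ending esketamine | Randomization |
| 6.3, general sentences | Any AE, with severity and attribution | Consent |
| 6.3, AE definition | Events associated with the presentation and follow-up sessions | – |
| Glossary | The same, plus events associated with esketamine treatment | – |
| 6.4 | Nausea, headache and hospitalization as examples of AEs | – |
| 8.7 | All adverse events reported by the PI | During the project |

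The scopes differ, and 6.3 gives two start points. Nausea and headache are AEs in 6.4, but they are also Appendix 2 items, which the note in 6.3 places outside the AE stream. Section 10 lists Appendix 2 as an adverse events form, whereas the appendix itself is titled a side-effects questionnaire.

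**Tracing one case: a serious event of a labelled type in a patient who continues esketamine**

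1. *6.3 list.* The event is covered only if it exceeds the label in severity or specificity. Otherwise no item applies.
2. *6.3 general sentences.* It is covered if it counts as an AE. Under the Glossary it clearly does. Under 6.3 it must be associated with the presentation or follow-up session. The TAU arm receives neither (section 4; Table 1), so for that arm the 6.3 definition, read literally, has almost nothing to attach to.
3. *Appendix 2 form.* The symptom is recorded if it is one of the 28 items and is elicited at either collection time: 24 hours after treatment 1, or the visit within 72 hours after treatment 8 (Table 1). The only response is None, Mild, Moderate or Severe. There is no field for seriousness, relatedness, onset or outcome, and a tick of Severe does not show that a patient was hospitalized. Section 7.4 allows the item to be reduced to present or absent.
4. *8.7 frequency rule.* This needs a count of events that are serious and at least possibly related, and an expected frequency to compare it with. Step 1 does not assure the count, step 2 leaves it to interpretation, and step 3 cannot supply it. Section 8.7 gives no expected frequency and says that no adverse events are anticipated, which sits badly with a rule about anticipated events.

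**Start point.** Randomization follows the screening visit and the eligibility check (6.1.1, 6.2). Section 6.1 allows up to 5 days to complete screening. The full interval from consent to randomization is not stated, so its length cannot be given.

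**The case against.** The strongest reply is that nothing is actually excluded. The list does not say that it is exhaustive. Section 6.3 says that any AE will be reported and recorded and that participants will be asked about AEs. Section 6.4 requires each AE to be documented with severity, relationship to the intervention and action taken, and names hospitalization. Section 6.5 asks withdrawing participants to return for assessment of AEs and SAEs. Section 8.3 enters expected adverse reactions in the database, and 8.7 has the PI report all adverse events. The greater-severity extension may also catch many serious labelled events, and the label is not in the documents, so the size of the remaining gap cannot be checked. The side-effect profile is compared between arms as an exploratory outcome, and the trial does not alter esketamine treatment.

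Much of this stands. A reader might infer that the plan collects nothing beyond the list, that a serious labelled event in a continuing patient is definitely lost, and that the 8.7 rule cannot be applied at all. The documents do not support that. Such an event may be captured by the general sentences, the extension or 6.4, and labelled symptoms are graded in both arms at two visits. The difference in start point also has little bearing on the arm comparison, because the presentation and the first esketamine treatment both come after randomization.

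What the reply does not remove is the conflict. The general sentences and 6.4 help only if the event counts as an AE, and the two definitions disagree on that. A list that names particular kinds of event has little purpose if every AE is collected anyway. The exploratory comparison rests on a form that cannot identify an event as serious or related.

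**Conclusion.** The point holds as a contradiction in the collection rules together with a missing express requirement. The 6.3 list disagrees with the general sentences in 6.3, with 6.4 and with 8.7. The AE definitions in 6.3 and the Glossary differ in whether they cover esketamine, and so in whether they apply to the TAU arm. No item requires all serious events to be collected. A serious labelled-type event in a patient who continues esketamine can be left with only an Appendix 2 tick, so the numerator for the 8.7 frequency rule is not assured and its comparator is not stated.

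The size cannot be put as a number of events, because the documents give no rates. The conclusion assumes that at least some events of labelled types can be serious without exceeding the label in severity or specificity, which cannot be checked without the label. The conflicts in definition and start point do not depend on that assumption. The matter concerns safety capture and leaves the CEQ-6 primary analysis untouched. It should be corrected, because whether a hospitalization is recorded as a serious event should not turn on which sentence of 6.3 a staff member follows.

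**What to change.** Three edits to the protocol:

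1. Add an item to the 6.3 list: all serious adverse events in either arm, whether or not labelled and whether or not esketamine is stopped, recorded on the SAE form with onset, seriousness criterion, relatedness and outcome. State that this includes any Appendix 2 item that meets a seriousness criterion.
2. Use one start point for collection in both 6.3 sentences.
3. Reconcile the 6.3 AE definition with the Glossary, so that a single definition applies to both arms. Bring the 6.3 list, 6.4 and 8.7 into line with it.

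These edits give 8.7 an assured count. They do not supply the expected frequency, which the plan would still need to state for that rule to be usable. They concern data capture only and change no treatment or clinical rule. The cost is a short amendment and a few extra entries, in 34 patients, on an SAE form that 6.3 already mentions.

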6.4 Reaction Management

Reaction management refers to the actions taken to manage any adverse events (AEs) that occur during the study. In the event that a participant experiences an AE, the study team will take appropriate measures to manage the reaction, minimize harm, and ensure the safety and well-being of the participant.

The first step in reaction management is to identify and document the AE. Participants will be asked to report any AEs they experience, either spontaneously or during the study visits.

The study team will document the AE, its severity, relationship to the intervention, and the actions taken to address it.

Based on the severity of the AE, the study team may take various actions to manage the reaction. For minor AEs, such as mild nausea or headache, the study team may provide advice or over-the-counter medications to alleviate the symptoms. For more serious AEs, such as hospitalization, the study team will take immediate action to ensure the safety and well-being of the participant.

If necessary, the study team may discontinue the intervention for a participant experiencing a serious adverse event. Participants who experience a serious adverse event will be referred to their treating physician or a specialist for further evaluation and management.

6.5 Withdrawal Procedures

The withdrawal procedure refers to the process for removing a participant from the study if they decide to discontinue their participation or they may be withdrawn at the discretion of the investigator at any time.

Participants may withdraw or be withdrawn from the study for various reasons, including adverse events, dissatisfaction with the study, personal circumstances, or inability of the subject to comply with the protocol-required schedule of study visits. In the event of a participant wishing to withdraw from the study, they will inform the study team.

The study team will inquire about the reason for withdrawal and document the reason and any relevant information related to the participant's decision. The investigator should also request the subject to return for an end-of-study visit to assess AEs/SAEs, safety endpoints, outcome events, and vital status. The investigator should also follow-up with the subject regarding any unresolved adverse events. Any unresolved events at the end of study or withdrawal should be followed for 2 weeks, until resolution, or until an adequate treatment plan is in place.

If the subject withdraws from the study and also withdraws consent for disclosure of future information, no further evaluations should be performed, and no additional data should be collected. Adequate documentation of this request should be obtained and retained in the subject's source file. True withdrawal of consent should be initiated by the subject and in writing. Data collected before the withdrawal of consent may be retained and used for analysis.

Patients who Withdraw from Treatment but not study

Participants may also decide to withdraw from the intervention but not the study for any reason. Or an investigator may withdraw a participant from the intervention for the following reasons:

- Significant study intervention non-compliance

- If any clinical adverse event (AE), or other medical condition or situation occurs such that continued participation in the study would not be in the best interest of the participant
- Medical condition which requires discontinuation of the study intervention
- If the participant meets an exclusion criterion (either newly developed or not previously recognized) that precludes further study participation
- Study termination

Subjects who sign the informed consent form and are randomized but do not receive the study intervention may be replaced. Subjects who sign the informed consent form, and are randomized and receive the study intervention, and subsequently withdraw, or are withdrawn or discontinued from the study, will not be replaced.

For participants who withdraw from treatment prior to 8th esketamine treatment and are not replaced, we will try to continue to collect the MADRS, the QIDS, and adverse events as indicated by study protocol.

If a participant withdraws from the study, they will no longer receive the intervention and the study team will ensure that the participant's privacy and confidentiality are maintained and that all personal information is handled in accordance with relevant regulations.

The study team will also ensure that any data collected from the participant up to the point of withdrawal is analyzed and reported in accordance with the study protocol.

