4.2 Outcome Variables/Endpoints

4.2.1 Primary Outcome Variables/Endpoints

Primary outcome: Group difference in change in question 6 of the CEQ-6 from baseline to after the presentation

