6.1 Study Procedures

Potential subjects will be referred to the study team by the interventional psychiatry physician who has seen the patient in clinical evaluation for esketamine, after ascertaining their agreement to be approached for the study. At this time, the patient will be reached out by a study team member and informed about the study.

Screening / Intake Visit

It is estimated the screening intake will take approximately 2 hours. It will consist of the following procedures and assessments and can be completed in up to 5 days:

- a. Informed Consent: A delegated study team member will discuss risks and benefits of participation and review the study overview with the patient as explained above. The patient will sign the informed consent form prior to any study procedures being performed.
- b. Clinical and Demographic Intake (including medical and psychiatric history, medication history, and current medications)
- c. Montgomery-Asberg Depression Rating Scale (MADRS) and Quick Inventory of Depressive Symptomatology (QIDS-SR16)
- d. CEQ-6 questionnaire regarding upcoming treatment course with esketamine
- e. Review of Inclusion/Exclusion Criteria by investigator

Presentation Visit (Intervention group only)

The intervention consists of a short virtual (via Zoom or similar technology) presentation provided to the participants, within 72 hours before the first treatment with esketamine. The presentation includes predetermined slides and content (the presenter will cover the same

slides and topics but will avoid a strict script to retain the personalized feeling of the presentation, an aspect believed to be crucial to the non-specific effects. Further, patients are allowed to engage, ask questions etc.) The presentation will remain factual and provide information from peer-reviewed literature. However, it is designed to convey a strong positive message, highlighting the effectiveness of the treatment. Additionally, a mild and temporary known side effect of the treatment (dysgeusia) will be intentionally highlighted to assess the 4th hypothesis.

Treatment visits:

Both groups will receive the usual treatment and care. Immediately before first and second treatments both groups will complete the CEQ-6 questionnaire. Additionally, the intervention group will complete the presentation feedback form prior to the first treatment. The rest of the treatments (i.e. treatments 3 to 8) will be done without any assessments.

Follow-up visit:

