7.7 Handling of Missing Data

Our primary analyses will be intent-to-treat using all available data. We will undertake sensitivity analyses to assess the impact of the missing response data on our conclusions. We will perform single-step (e.g., missing values on the response variable replaced by predicted values from linear or generalized linear models of the longitudinal data over time) or multiple imputation and compare the performance of the imputed data results compared to complete case analyses. It is important to note that the linear mixed model method we propose to use is valid under the assumption that missing data is missing at random (MAR). Since it is not possible to test the MAR assumption and since for every MNAR model there is an equally well-fitting MAR model, we believe that the only suitable approach is to perform sensitivity analyses according to different plausible scenarios for missing data and make sure the conclusions are consistent. If the results are not consistent depending on the assumptions for missing data we will report the conclusions based on each set of assumptions.

8 Data/Specimen Handling and Record Keeping

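### Two minor repairs: section 7.7 allows single predicted-value imputation in the sensitivity analyses, and the continued-collection list in 6.5 leaves out the CEQ-6 and replaced participants

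*Combined protocol and SAP*

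**What the plan says.** **Imputation.** Section 7.7 states: "Our primary analyses will be intent-to-treat using all available data". For sensitivity analyses it then offers two ways to fill missing responses: a single step using predicted values from a linear or generalized linear model, or multiple imputation. The filled-in results are to be compared with complete cases.

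**Replacement and collection.** Section 6.5 states: "Subjects who sign the informed consent form and are randomized but do not receive the study intervention may be replaced". For participants who stop before the eighth esketamine treatment "and are not replaced, we will try to continue to collect the MADRS, the QIDS, and adverse events". The CEQ-6 is not in that list. The same section keeps data already gathered: "any data collected from the participant up to the point of withdrawal is analyzed and reported in accordance with the study protocol", and "Data collected before the withdrawal of consent may be retained and used for analysis".

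**Primary measure.** Section 4.2.1 defines the outcome as "Group difference in change in question 6 of the CEQ-6 from baseline to after the presentation". Section 6.1 says: "Immediately before first and second treatments both groups will complete the CEQ-6 questionnaire". In Table 1 the CEQ-6 immediately before treatment 1 is the only one scheduled between the presentation and the first dose. The end-of-study visit has no CEQ-6. Section 6.1 labels the presentation "Presentation Visit (Intervention group only)", and section 6.1.1 places it after randomisation.

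**The concern.** The two points are separate.

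1. A predicted value lies exactly on the fitted line. Analysing it as if it had been observed removes the scatter that a real value would carry and counts a person who supplied no response. Standard errors become too small. A sensitivity analysis is meant to show whether conclusions survive missing data, and this version can look more certain than the data allow.

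2. TAU has no presentation to miss, so missing it is an event after randomisation in one arm. Section 5.3 notes that study participation does not decide whether esketamine is given, so a person can miss the presentation and still attend treatment 1. If the site took the 6.5 list as the full instruction for such a person once replaced, it might not collect the CEQ-6 that day, whereas the same kind of person in TAU would complete it. If these people would have reported a smaller rise in expectation anyway, the comparison would lean towards the intervention with no true effect.

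**Working it through.** The plan states no missing-data rate, non-receipt rate, CEQ-6 SD or correlation, so there is no figure of its own to reproduce on this point. From the documents come 17 per arm (5.2, 7.1) and two-sided 0.05 (7.2). Everything else below is assumed.

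**Point 1: single predicted-value imputation**

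Assumptions: baseline and follow-up each have SD 1 and correlation 0.5; k of 17 follow-up values are missing completely at random in each arm; prediction is from baseline and group; a t-test is applied to change. On completed data with two timepoints, that t-test equals the group-by-time test.

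The residual variance given baseline is 1 − 0.5² = 0.75. The part of the change variance due to baseline is (0.5 − 1)² = 0.25.

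- Variance of an arm mean that the test assumes: [0.75 × (17 − k)/17 + 0.25]/17
- Actual variance, approximately: 0.75/(17 − k) + 0.25/17

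For k = 4:
- Assumed: (0.75 × 13/17 + 0.25)/17 = 0.0484
- Actual: 0.75/13 + 0.25/17 = 0.0724
- Standard-error ratio: √(0.0484/0.0724) = 0.82

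The same sums give 0.96 for k = 1, 0.91 for k = 2 and 0.86 for k = 3. Simulation under no effect (40,000 runs; 8,000 with 20 imputations for multiple imputation) gave:

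| Missing per arm | SE ratio | Type I error, single prediction |
|---|---|---|
| 1 | 0.96 | 6.0% |
| 2 | 0.91 | 7.7% |
| 3 | 0.86 | 9.0% |
| 4 | 0.82 | 11.2% |

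For the same range, complete cases gave 4.9 to 5.2% and multiple imputation 4.5 to 4.8%. Repeat runs of the single-prediction case gave 6.0 to 6.2%, 7.2 to 7.7% and 11.0 to 11.4% for 1, 2 and 4 missing.

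**Point 2: loss from one arm**

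Assumptions: k of 17 + k intervention participants miss the presentation, are not assessed and are replaced. The same fraction f = k/(17 + k) of TAU would have missed it but is assessed, and changes D SD less. There is no true effect, the change-score SD is 1, and the test is a t-test with 100,000 runs. Bias = f × D.

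| k | f | Bias, D = 0.5 / 1 | Type I error, D = 0.5 / 1 |
|---|---|---|---|
| 1 | 1/18 = 0.056 | 0.03 / 0.06 SD | 5.1% / 5.2% |
| 2 | 2/19 = 0.105 | 0.05 / 0.11 SD | 5.3% / 6.0% |
| 4 | 4/21 = 0.190 | 0.10 / 0.19 SD | 5.8% / 8.0% |

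Three comparisons isolate the cause.

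- Same fraction lost and nobody replaced: the bias is unchanged (k = 2: 0.05 / 0.11 SD; k = 4: 0.10 / 0.19 SD). Replacement is therefore not the source.
- Same people lost from both arms, or D = 0: bias is 0.00 SD.
- Everyone assessed and kept: bias is 0.00 SD and type I error does not exceed 5% beyond simulation error.

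If only half of such people would have been assessed in TAU, the bias halves (k = 2: 0.03 / 0.05 SD).

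**The case against.** **A reader might infer that replacement conflicts with intent-to-treat, or that replaced participants are dropped.** The documents do not support this. Replacement adds enrolment; intent-to-treat governs analysis. Section 7.7 keeps all available data, 6.5 keeps data gathered before withdrawal, and nothing excludes a replaced participant. Replacement is also discretionary.

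**The collection gap may not exist in practice.** Section 6.1 has both groups complete the CEQ-6 before treatment 1 without condition, and 6.5 provides for leaving the intervention while staying in the study. The 6.5 list refers to stopping before the eighth esketamine treatment, so it may concern the esketamine course and not a missed presentation. If the replacement rule is aimed at people who never start treatment, it applies to both arms and the bias disappears. All of this is fair. What stands is that the section uses treatment and intervention loosely, ties continued collection to not being replaced, and omits the primary measure.

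**The calculation is not the planned analysis.** This is correct. The plan specifies a linear mixed model, in which a baseline-only participant still contributes. In an illustration where loss depended only on baseline (correlation 0.5; 2 or 4 lost from one arm), complete-case bias was 0.09 or 0.16 SD in size, and adjustment using the retained baselines brought it to about zero. Such a model would not remove bias from unrecorded reasons for missing the presentation.

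**The imputation choice touches only sensitivity analyses.** This is also correct. A reader might take 11% as the trial's type I error, and it is not. Multiple imputation is already offered, and inconsistent results are to be reported. But the plan leaves the choice open, and one of the two options is known to understate error.

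**Conclusion.** Both points are minor.

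The imputation point is the firmer. Under the stated assumptions, single prediction raises type I error to about 6%, 7 to 8% and 11% with 1, 2 and 4 of 17 missing per arm, against about 5% for complete cases. It affects sensitivity analyses only; the primary mixed-model result does not change.

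The collection point is a gap between the general CEQ-6 schedule in 6.1 and a narrower list in 6.5. Harm requires that the narrower list is followed, that the loss falls on one arm, and that those lost differ. For one or two people the bias is then 0.03 to 0.11 SD with type I error of 5.1 to 6.0%. The 8.0% figure needs four of 21 to miss the presentation and to change a full SD less. These sizes rest wholly on assumed inputs and a change-score t-test.

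**What to change.** - **Section 7.7:** delete the single-step predicted-value option and use the multiple imputation already named there.
- **Section 6.5:** remove the restriction of continued collection to people who are not replaced, and add the CEQ-6 to the list. State that the CEQ-6 before treatment 1 is sought from every randomised participant unless consent is withdrawn, whether or not the presentation was given, and that each is analysed in the assigned arm.

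The cost is a few sentences. No visit or instrument is added, because 6.1 already schedules that questionnaire for both groups. Keeping non-receivers does dilute the effect: with an assumed 1 SD effect in receivers and none in non-receivers, power falls from 81% to 75% with one kept and 69% with two, if nobody is added. That loss already follows from the intent-to-treat rule in 7.7 and is not a cost of this change.
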